#### **10.1.5 Best Corrected Visual Acuity (BCVA)**

BCVA will be listed by cohort treatment groups and visit for both Snellen Equivalent and logMar measurements under standard lighting condition (both Part 1 and 2) and low luminance condition (Part 2 only). Potentially clinically significant findings under the standard lighting condition will be flagged according to the following category:

- Change from baseline is  $\geq 15$  letters improvement or worsening (logMar)

#### **10.1.6 Other Safety Analysis**

A number of safety measures, for example: Clinical Laboratory Test, Urine Pregnancy Test, Physical Examination, Visual Fields, Macroscopic Hyperemia, Dilated Fundus Examination, Pupil Size, and Subject Comfort will only be presented in the listing.

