**Statistical Method for primary endpoint:**

In general, data will be summarized with descriptive statistics which will include sample size, mean, standard deviation, median, minimum and maximum for continuous variables and frequency and percentage for categorical variables.

The Medical Dictionary for Regulatory Activities (MedDRA) nomenclature will be used to code adverse events. The number and percentage of subjects with adverse event reports will be tabulated for all treatment-emergent adverse events (TEAEs) regardless of causality, treatment-related TEAEs, all serious TEAEs, treatment-related serious TEAEs, and all adverse events leading to premature discontinuation of study treatment.

[figure not shown]
Analysis populations: Each population will be analyzed based on the treatment received.

- Part 1: The Safety population consisting of all treated subjects will be used for all analyses. All safety and IOP-lowering effects tabulations will provide descriptive statistics by cohort.
- Part 2: The Safety population, as defined above, will be used for analyses of all Safety data. In addition to the Safety population two other populations are defined for analyses of Part 2 efficacy data:

The Modified Intent-to-treat (mITT) will consist of all randomized and treated subjects who provide IOP data at baseline and at least one post-baseline IOP assessment. This population will be used for analyses of efficacy data.

The Per-protocol (PP) population is a subset of the mITT population and will consist of subjects who did not have any major protocol violations deemed to have potential impact on the primary endpoint. This population will be used to confirm the primary efficacy analysis.

The primary efficacy endpoints are the Day 14/Exit mean IOP changes from Baseline (Day - 1) at each time-matched hour (0, 2, 4, 8) in the study eye. The primary efficacy analysis will be within-group mean change from baseline IOP at hour 2, the time of peak effect of timolol. Between treatment group comparative analyses will be performed in the mITT population via analysis of covariance (ANCOVA) tests which will have treatment as the main effect and the baseline hour-matched IOP as the covariate in the model. Pairwise treatment group comparisons will be performed for each individual dose of AGN-227535 ophthalmic solution versus timolol ophthalmic solution 0.5%. Confidence intervals (95%) based on this ANCOVA model will be provided for the differences between treatment groups.

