[figure not shown]
[figure not shown]
[figure not shown]
[figure not shown]

Additional safety analyses will include evaluation of peak severity of macroscopic hyperemia and hyperemia as evaluated on biomicroscopy at each post-baseline visit (Days 4 and 14) and across all post-baseline time points.

**Sample Size Calculation:** For each cohort in Part 1 of the study a sample size of 6 patients will provide 83% power to detect a 3 mm Hg within-group change from pre-dose assuming a standard deviation of 2 and two-sided alpha = 0.05.

Part 2 sample size will provide >90% power to detect within-group and between-group treatment differences of mean change from baseline of at least 3 mm Hg for the primary endpoint assuming a standard deviation of 2.5 with two-sided alpha = 0.05. With a treatment group difference of -1 mmHg, the power ranged from 50% for a common SD of 3.5 to 78% for a common SD of 2.5 to conclude non-inferiority based on a 1.5 mmHg margin and a 1-sided alpha = 0.025.

**Data Monitoring Committee:** No formal Data Monitoring Committee is planned. Between dose-escalation groups in Part 1, all available data collected to date will be used to assist in decision making to continue to the next dose or to stop the study. All data collected in Part 1 will be used to select 1 or 2 concentrations of AGN-227535 to evaluate in Part 2. The decision to proceed or to stop the study will be made by the Medical Monitor, the Head of Clinical and the Chief Executive Officer. All decisions will be documented.

**Figure 1 Schematic of Study Design****Figure 2 Part 1 Dose Escalation****Visit Flow****Dose Escalation****Figure 3 Part 2 (Parallel Comparison)****Visit Flow**

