### **9.3.2. Safety Analyses**

All safety analyses will be performed on the Safety Population.

The Medical Dictionary for Regulatory Activities (MedDRA) nomenclature will be used to code adverse events. A detailed definition of treatment emergent adverse events (TEAEs) will be provided in the SAP. The number and percent of subjects with adverse event reports will be tabulated for all treatment emergent adverse events (TEAEs) regardless of causality, treatment-related TEAEs, all serious TEAEs, treatment-related serious TEAEs, and all adverse events leading to premature discontinuation of study treatment.

For Part 2, analyses of macroscopic hyperemia and hyperemia as evaluated on biomicroscopy will include evaluation of peak severity at each post-baseline visit (Days 4 and 14) and across all post-baseline time points.

Detailed methods for analyses of all safety variables will be provided in the SAP.

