## **10 SAFETY ANALYSIS**

Listings will be presented for all of the safety parameters (section 5.4) for Part 1 and 2 of the study, with the exception of adverse events, which will be summarized as described below. For slit-lamp biomicroscope and visual acuity parameters, potentially clinically significant findings will be flagged according to pre-defined criteria in the listings.

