#### **10.1.3 Biomicroscopy**

Slit-lamp biomicroscopy will be listed for Part 1 and 2 of the study by cohort treatment groups. Parameters with positive (no zeros or missing) findings will be presented. At any timepoint, a parameter will be omitted if there is no positive finding on either eye. Potentially clinically significant findings will also be flagged on the following category:

- Hour-matched change from baseline is of  $\geq 2$  grade worsening

The biomicroscopy Case Report Form (CRF) includes multiple categories, each of which includes multiple parameters to be evaluated. If the CRF's leading question "Were there any biomicroscopic findings?

(Yes/No)" is answered "No", then all parameters in all categories are to be treated as zero score or negative grade, even though they will show as "missing" in the database. If the CRF's leading question is answered "Yes", then the leading question of each category "Were there any /category/ findings (Yes/No)?" must be answered. If the category's leading question is answered "No", then all parameters in the category are to be treated as zero score or negative grade, even though they will show as "missing" in the database. Thus, a parameter with a "missing" value in the database will be treated as either zero score or negative grade under either of the two conditions below:

1. When the CRF's leading question about any biomicroscopic findings is answered "No".
2. When the CRF's leading question about any biomicroscopic findings is answered "Yes" and the category's leading question about any findings is answered "No".

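### The SAP plans no output for the peak hyperemia severity that the protocol names for Part 2, and SAP 1.1 does not declare the change

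*SAP*

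**What the plan says.** **Part 2 hyperemia.** Protocol 9.3.2 states that "analyses of macroscopic hyperemia and hyperemia as evaluated on biomicroscopy will include evaluation of peak severity at each post-baseline visit", names Days 4 and 14, and adds an evaluation over all post-baseline time points. The synopsis repeats this as an additional safety analysis. Protocol 9.3.2 then says: "Detailed methods for analyses of all safety variables will be provided in the SAP".

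SAP 10 sets the general rule: "Listings will be presented for all of the safety parameters (section 5.4) for Part 1 and 2 of the study", with adverse events as the exception. SAP 10.1.6 says of several measures that "Macroscopic Hyperemia, Dilated Fundus Examination, Pupil Size, and Subject Comfort will only be presented in the listing". On the slit lamp, SAP 10.1.3 says: "Slit-lamp biomicroscopy will be listed for Part 1 and 2 of the study by cohort treatment groups". It adds a flag for an hour-matched worsening of two or more grades.

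**Part 1.** Protocol 9.3 and the synopsis say: "All safety and IOP-lowering effects tabulations will provide descriptive statistics by cohort". SAP 6.2 confines descriptive statistics for IOP and adverse events to Part 2. SAP 9 gives listings for Part 1 IOP. SAP 10.1.1 rules out a Part 1 adverse event summary. SAP 10.2 says that Part 1 IOP summary data, as set out in section 9, and listings or tabulations of other data will be supplied for dose decisions if needed.

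**Declared changes.** SAP 1.1 restricts itself to Part 2 and names three items: the per-protocol analysis, the two-way ANOVA with baseline IOP stratum, and the descriptive statistics by stratum.

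**The concern.** The protocol leaves the method of the hyperemia analysis to the SAP, but it fixes that peak severity will be part of that analysis. A SAP that offers only listings has not chosen a method. It has removed a named evaluation, and the section where a reader would look for that says nothing.

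Ocular tolerability is part of the study objective (SAP 2), and hyperemia is graded by two methods throughout Part 2. The treatment-emergent adverse event tables by treatment group give a partial view of tolerability, but they count reported events at their highest severity, not examination grades. If the peak is not defined in advance, anyone who later wants the protocol's evaluation must settle its rules after the randomization has been released.

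For Part 1, the question is whether the first-in-human IOP and adverse event data receive any routine summary by cohort.

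**Working it through.** The main point is a comparison of texts, and no figure in the plan needs correcting.

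| Item | Protocol | SAP |
|---|---|---|
| Part 2, macroscopic hyperemia | Peak severity at Day 4, at Day 14 and over all post-baseline times (9.3.2, synopsis) | Listing only (10.1.6) |
| Part 2, hyperemia on slit lamp | The same three periods | Listing of positive findings, with a flag (10.1.3) |
| Part 1, IOP | Tabulations give descriptive statistics by cohort (9.3, synopsis) | Listings (9); descriptives for Part 2 only (6.2) |
| Part 1, adverse events | The same sentence | No summary (10.1.1) |
| Declared in SAP 1.1 | Not applicable | None of the above |

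**Size of the Part 2 gap.** 2 methods × 3 periods (Day 4, Day 14, all post-baseline) = 6 named evaluations without planned output.

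**Does the slit-lamp flag stand in for the peak?** No.
- SAP 10 provides flags for slit-lamp and visual acuity parameters only, so macroscopic hyperemia has none.
- The flag marks an hour-matched change above a threshold. It does not give the worst grade in a period.
- Exclusion criterion 33 requires hyperemia below +1 at Baseline Hour 0. The macroscopic scale runs 0, +0.5, +1, +2, +3, and the slit-lamp hyperemia scale is not shown. If it has the same steps (an assumption), a rise from 0 to +1 is one unit, or two steps on the scale. SAP 10.1.3 does not say which of these a grade is.

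**Does the peak need a definition?** Yes. Protocol Table 3 schedules both methods on Day 1 at Hour 0, at 30 minutes and at Hour 2, and on Days 4 and 14 at Hours 0, 2, 4 and 8. Per eye and method that is 3 + 4 + 4 = 11 gradings. SAP 9.1 places baseline on Day -1, so Day 1 Hour 0 is post-baseline but still pre-dose. Leaving it out gives 11 − 1 = 10. Both eyes are examined, so it must also be settled whether the peak is per eye or per subject.

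**Part 1.**
- Protocol 9.2 sizes each cohort on a within-group IOP change: n = 6, change 3 mm Hg, SD 2, two-sided alpha 0.05, stated power 83%. With a noncentral t, df = 6 − 1 = 5 and noncentrality = (3/2) × √6 = 3.67, the power is 83.3%, so the figure reproduces. At SD 2.5 it is 65.5%, against a stated bound of 66%. The conclusion does not rest on this; it shows only that the protocol had a mean change by cohort in view.
- The adverse event tabulation in Protocol 9.3.2 is not limited to one part, whereas the hyperemia sentence after it is limited to Part 2. This favours reading the protocol as expecting Part 1 adverse event counts.
- SAP 10.2 sends the reader to section 9 for Part 1 IOP summary data. Section 9 offers Part 1 listings only, so the cross-reference has no target.

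**The case against.** **The SAP is entitled to set the safety methods.** It is, and the protocol prescribes no table layout. But delegated detail does not extend to dropping an evaluation that the protocol says will be included.

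**The Part 1 sentence may govern only whatever tabulations are made.** This is a fair reading. On it, the protocol requires no particular Part 1 table, and SAP 10.2 offers summaries if they are needed. With about 6 subjects per cohort, full listings also show every value, so the practical loss is small. Against it, Protocol 9.3 opens by saying that data in general will be summarized descriptively, and the narrow reading leaves the sentence with no Part 1 IOP or adverse event table to govern. The Part 1 point therefore stays secondary and arguable. The faulty cross-reference stands on either reading.

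**Stronger readings that the documents do not support:**
- A reader might infer that a planned comparison of hyperemia with timolol was lost. The protocol's hyperemia sentences name an evaluation of peak severity, without an arm comparison or a test. Only the general Part 2 wording in Protocol 9.3 could supply one.
- A reader might infer that the listings bury the peak under a very large number of grades. For the slit lamp, SAP 10.1.3 says: "Parameters with positive (no zeros or missing) findings will be presented". The subject numbers are also approximate, with replacement allowed, so no firm ceiling on the number of grades can be given.
- A reader might infer that a zero grade cannot be told from a missed examination. The layout of the listing is not given, and the leading questions on the case report form separate the two in the data.
- A reader might infer concealment. The SAP states its listings-only approach openly in sections 9, 10, 10.1.1, 10.1.3 and 10.1.6. The defect is an incomplete section 1.1.

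**Conclusion.** The Part 2 point holds. Six protocol-named evaluations of peak hyperemia have no planned output in the SAP, and SAP 1.1 does not declare the departure. The Part 1 point is real but weaker: the SAP plans no routine IOP or adverse event summary by cohort, the protocol sentence can be read narrowly, and SAP 10.2 refers to content that section 9 lacks.

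The consequence is limited. The trial is exploratory, no efficacy conclusion changes, Part 2 adverse events are tabulated by treatment group, Part 1 demographics are summarized, and all individual data remain listed. This should be corrected, but it does not threaten the trial's main result. The conclusion assumes that the visible SAP text is complete on hyperemia and that no separate table specification adds the missing summaries.

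**What to change.** In SAP 10, add descriptive Part 2 summaries by treatment group of peak macroscopic and peak slit-lamp hyperemia, at Day 4, at Day 14 and over all post-baseline time points. State:
- whether the peak is per eye or per subject;
- the denominator, for example the number examined in the period;
- whether the pre-dose Day 1 Hour 0 grade counts;
- that the zero-coding rules of SAP 10.1.3 apply to the slit-lamp grades.

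The layout is for the SAP to choose; counts and percentages per grade would do.

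For Part 1, add short descriptive statistics by cohort for IOP change and adverse events to SAP 9 and 10 and correct the reference in SAP 10.2. Alternatively, declare and justify the omission in SAP 1.1, extended to cover Part 1. If any of the hyperemia evaluations is still to be dropped, that also belongs in SAP 1.1.

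The cost is one SAP revision and a few descriptive tables from data already collected. Because the protocol already names the hyperemia evaluation and leaves its method to the SAP, no protocol amendment is needed. The documents do not show whether the database has been locked; if it has, the added tables should be labelled as post-lock.

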### **10.2 Data Monitoring**

No formal Data Monitoring Committee is planned. Between dose-escalation groups in Part 1, all available data collected to date will be used to assist in decision making to continue to the next dose or to stop the study. All data collected in Part 1 will be used to select 1 or 2 concentrations of AGN-227535 to evaluate in Part 2. The decision to proceed or to stop the study will be made by the Medical Monitor, the Head of Clinical and the Chief Executive Officer. All decisions will be documented. If needed, IOP summary data as described in Section 9 and data listings or tabulations of non-IOP data for Part 1 will be provided for the decision-making purpose.

## **11 VALIDATION**

Derived datasets will be independently reprogrammed by a second programmer. The separate datasets produced by the two programmers must match 100%. Tables and listings will be independently reprogrammed by a second programmer for numeric results. Statisticians will be involved in the process of programming and validating tables that include inferential statistical results.

## 12 GLOSSARY OF ABBREVIATIONS

ANOVA	Analysis of Variance
ATC	Anatomical Therapeutics Chemical
BCVA	Best Corrected Visual Acuity
bpm	Beats Per Minute
CRF	Case Report Form
ECG	Electrocardiogram
IOP	Intra-ocular Pressure
IWRS	Interactive web-response system
LOCF	Last Observation Carried Forward
MedDRA	Medical Dictionary for Regulatory Activities
Mm Hg	Millimeters of mercury
MITT	Modified Intent-to-Treat
OD	Right Eye
OHT	Ocular Hypertension
OS	Left Eye
POAG	Primary Open Angle Glaucoma
PP	Per Protocol
PR	Pulse Rate
PT	Preferred Term
SAP	Statistical Analysis Plan
SAE	Serious Adverse Event
SD	Standard Deviation
SOC	System Organ Class
SOP	Standard Operating Procedure
TEAE	Treatment-Emergent Adverse Event
WHO	World Health Organization

## 13 VERSION HISTORY

Version	Date	Details
1.0	18 Feb 2021	SAP Approval
2.0	02 Mar 2021	

• Section 13 added

• Table of Contents Refreshed

